10.3.3 Referral to tertiary services related to the tracer conditions

These referrals are defined in Appendix. These will be reported as separate outcomes for each tracer condition, using the relevant subpopulation for that tracer condition.

10.3.4 All Outpatient Referrals

We will also analyse an outcome including all outpatient referrals, to account for possible increase in referrals due to the detection of unmet need.

10.4 Emergency department (ED) attendance

An ED attendance is a child’s health contact at the emergency departments at St Thomas’s, Guy’s or Kings College Hospitals.

Include:

- Self-referral when the parent or carer feels the child’s condition is serious enough to warrant emergency care
- GP referred
- Attendance at Guy’s Hospital Urgent Care Centre (Department type 3)
- Attendance at St Thomas’s (ED Department type 1 (a consultant-led 24-hour service))
- Attendance at KCH

Exclude:

- Planned attendances, attendance category = 2 (Unplanned Follow-up Emergency Care Attendance for the same or a related clinical condition and within 7 days of the First Emergency Care Attendance at the same Emergency Care Department), Follow-up Accident and Emergency attendance – planned

ED attendance rates

The rate of ED rates will be measured as count per patient-year.

10.5 Outpatient appointment attendances

The rate of Outpatient appointment attendances will be measured as count per patient-year.

We will consider two sets of outpatient attendances:

10.5.1 Attendance of General Paediatrics Outpatient appointment

These are defined using the terms in Appendix. This outcome will be used for the “Health Service Use Population-level population” (as defined in section 8.1).

10.5.2 Attendance of General Paediatrics Outpatient and Tertiary services related to the tracer conditions

Rationale: If CYPHP is improving health, or through offering early intervention for asthma/eczema/constipation, we hypothesize there will be fewer general paediatrics and tertiary service referrals for these conditions. These attendances are defined in Appendix. This outcome will be used for “Health Service Use Population-level population” (as defined in section 8.1).

10.5.3 Attendance of tertiary services related to the tracer conditions

These attendances are defined in Appendix. These will be reported as separate outcomes for each tracer condition, using the relevant subpopulation for that tracer condition.

10.5.4 All Outpatient Attendances

We will also analyse an outcome including all outpatient attendances, to account for possible unintended consequences of intervention.

10.6 Ambulatory care sensitive admissions

Ambulatory care sensitive (ACS) conditions are conditions where effective primary care and case management can help prevent the need for hospital admission.

10.6.1 Standard definition of ACS admissions

ACS chronic conditions, in CYP, are asthma, diabetes and epilepsy. ACS infectious illnesses are vaccine-preventable conditions, gastroenteritis, lower and upper respiratory tract infection, and urinary tract infection in all children (Cecil 2018, AHRQ, NHS Digital). These admissions will be extracted using ICD-10 codes listed in Appendix, recorded in the primary diagnosis of patient records.

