9.1 Primary and secondary health service use

Activity data collected on all CYP's contacts with the health care system

1. **Non-elective admission rates (Primary outcome)**
2. Primary care consultation rates
3. Primary care outpatient appointment referrals
 - a. All
 - b. Referrals relating to tracer conditions
4. Emergency department attendance
5. Outpatient appointment attendances
 - a. All
 - b. Appointments relating to tracer conditions
6. Ambulatory care sensitive admissions
7. Proportion of non-elective admissions that are ambulatory care sensitive
8. Rate (sum per patient-year) of non-elective admissions and outpatient appointment attendances, combined

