10. HEALTH SERVICE USE OUTCOME DEFINITIONS AND ANALYSIS METHODS

10.1 Non-elective hospital admission (NEA) rates (Primary population outcome)

We will determine non-elective admissions from admitted care data, of CYP aged <16 years, registered with Lambeth and Southwark GP practices, admitted to St Thomas's, Guy's or King's College Hospitals. Admitted patient care is recorded in episodes. An episode is a record of an individual patient's care with a single consultant, within a hospital provider, and forms all or part of an overall hospital spell (an admission). Each episode contains data on the patient (age, area of residence and registered GP practice code); on the episode of care (the date of admission and method of admission - whether the admission was elective or non-elective); and clinical information. Diagnoses for each patient are recorded using the International Classification of Diseases, 10th edition (ICD-10) and the information is divided into the primary diagnosis (main problem treated) and various secondary diagnoses (including comorbidities and complications). Procedures performed during an episode are coded using the Office of Population, Censuses and Surveys Classification of Surgical Operations and Procedures, 4th revision (OPCS4).

We will select the dominant episode record for each admission and check for duplicate data using a combination of patient ID (pseudonymised) and admission date. We will calculate length of stay (days) as the date of discharge–date of admission.

A non-elective admission is an unplanned event and occurs when a consulting clinician determines a child's presenting condition is serious and requires immediate hospital care. Children who have well managed health conditions are less likely to experience a non-elective admission.

A non-elective admission is determined in Admission Method field as codes 21-25, 2A, 2B, 2D, 28. (See table in Appendix.)

NEA rates

Non-elective hospital admission (NEA) rate will be measured as number of events per patient-year in each GP practice.

The numerator is the number of NEA per GP practice and denominator is person-years of GP registered population under age 16. The numerator will be taken from GSTT and KCH data.

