10.7 Proportion of non-elective admissions that are ambulatory care sensitive

Use definition above to define ACS admissions.

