23.11 Ambulatory care sensitive admission ICD-10 codes

Description	ICD-10 codes
Chronic conditions	
Asthma	J45, J46
Diabetes	E10-E14
Epilepsy	G40, G41
Acute infections	
Lower respiratory tract infections	J10.0, J11.0, J11.1, J12-J16, J18.0, J18.1, J18.9, J21
Upper respiratory tract infections	H66, H67, J02, J03, J04.0, J06, J31.2
Dehydration and gastroenteritis	E86, K52.2, K52.8, K52.9, A02.0, A04, A07.2, A08.0, A08.1, A08.3, A08.4, A08.5, A09
Urinary tract infections	N10-N12, N13.6, N15.9, N30.0, N30.8, N30.9, N39.0
Other	
Vaccine-preventable diseases	A35-A37, A80, B05, B06, B16.1, B16.9, B18.0, B18.1, B26, G00.0, M01.4

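### Outcome 6 (ambulatory care sensitive admissions) is selected by primary diagnosis alone, so planned admissions with a listed code are counted

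*SAP*

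**What the plan says.** Section 10.6 introduces ACS conditions as "conditions where effective primary care and case management can help prevent the need for hospital admission". Section 10.6.1 then gives the selection rule: "These admissions will be extracted using ICD-10 codes listed in Appendix, recorded in the primary diagnosis of patient records". Section 10.6.2 adds eczema to the list and otherwise inherits that rule. The table in appendix 23.11 gives ICD-10 codes by condition and has no admission-method column.

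The data come from the admitted-care extract described in section 10.1, where each episode records "the date of admission and method of admission - whether the admission was elective or non-elective". For the primary outcome, that section turns the field into a filter: "A non-elective admission is determined in Admission Method field as codes 21-25, 2A, 2B, 2D, 28". Appendix 23.6 describes the same codes.

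Section 10.7 and item 7 of section 9.1 carry the title "Proportion of non-elective admissions that are ambulatory care sensitive". The only text under 10.7 is "Use definition above to define ACS admissions".

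**The concern.** The SAP has two tools for classifying an admission: the diagnosis code and the admission method. It uses the second for the primary outcome but only the first for outcome 6. An analyst who programs 10.6.1 literally will count an elective admission with epilepsy, diabetes or another listed code as primary diagnosis alongside emergency admissions for the same condition.

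The purpose stated in 10.6 is to capture admissions that good primary care can help avert. A planned admission is usually a decision about investigation or treatment, and there is no particular reason to expect the CYPHP model to reduce it. If such events form part of the count and do not respond to the intervention, they pull the rate ratio towards 1. What is at stake is a somewhat weakened contrast on a secondary outcome, and an outcome whose content does not quite match its name.

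**Working it through.** **Step 1: is there an admission-method condition anywhere in the ACS definition?**

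| Place in the SAP | Condition on diagnosis | Condition on admission method |
|---|---|---|
| 9.1, item 6 | by name only | none |
| 10.6 | concept only | none |
| 10.6.1 | listed ICD-10 code, primary diagnosis | none |
| 10.6.2 | as 10.6.1, plus eczema | none |
| Appendix 23.11 | code list | none |
| 10.1 and appendix 23.6 (primary outcome) | none | 21-25, 2A, 2B, 2D, 28 |
| 9.1, item 7, and the title of 10.7 | ACS | non-elective, stated in the title |

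In section 9.1 the word non-elective is written into items 1, 7 and 8 but not item 6. Where the SAP wants the restriction, it says so. The natural reading of 10.6.1 is therefore all admissions with a listed primary diagnosis.

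**Step 2: how much could it matter?** The SAP gives no figure for outcome 6 to reproduce, so this is an illustration only. Inputs:

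- *e*, the share of ACS-coded admissions that are elective without the intervention. The SAP does not give it. Assumed 5% to 15%, with 30% as an outer value.
- The true rate ratio for non-elective ACS admissions. Assumed 0.80. The 20% reduction in section 5.1 refers to all non-elective admissions, so 0.80 is not a design figure for this outcome.
- The rate ratio for elective admissions. Assumed 1, meaning unaffected.

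The observed ratio is the mixture 0.80 × (1 − *e*) + 1 × *e*:

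- *e* = 0: 0.80 (the result with the filter in place)
- *e* = 0.05: 0.80 × 0.95 + 0.05 = 0.76 + 0.05 = 0.81
- *e* = 0.15: 0.80 × 0.85 + 0.15 = 0.68 + 0.15 = 0.83
- *e* = 0.30: 0.80 × 0.70 + 0.30 = 0.56 + 0.30 = 0.86

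Over the 5% to 15% range, a true 20% relative reduction would appear as 19% to 17%.

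**Step 3: does the gap carry into 10.7?** The title describes a classification within non-elective admissions: of those, the share that are ACS. The text beneath it tells the analyst which of them to label ACS. Read together, the numerator is admissions that are both non-elective and ACS-coded, and the denominator is all non-elective admissions. That is a proper proportion.

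**The case against.** The best case for leaving the text alone has four parts.

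First, 10.6.1 is headed as a standard definition and cites sources, which may themselves restrict to emergency admissions. The outcomes-and-populations table (appendix 23.1) and the data and reporting guidelines are separate files and might do so too. None of these can be checked here. Reference 9 merely repeats the source names without a title or version, so the restriction cannot be recovered from the SAP. This tempers the point: what can be said is that the rule as written does not exclude planned admissions.

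Second, the concept in 10.6 speaks of hospital admission without saying non-elective, so counting every admission is not a contradiction. That is fair. The case for the filter rests on the purpose of the outcome, not on an inconsistency.

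Third, most rows of appendix 23.11 are acute infections or vaccine-preventable diseases, for which planned admission is not an obvious route. Only asthma, diabetes and epilepsy are listed as chronic. The elective share could be at or below the low end of the assumed range. This stands, and it is why the size is described as modest.

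Fourth, a reader might infer two stronger faults that the document does not support. One is that the numerator of 10.7 may fall outside its denominator. That would happen only if an analyst ignored the outcome's title and divided the 10.6 count by the 10.1 count. The other is that the intervention could raise planned admissions and so reverse the apparent effect. The SAP does anticipate a possible rise in outpatient referrals through detection of unmet need (10.3.4), but nothing in it says that the model brings forward planned inpatient stays.

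**Conclusion.** The point holds for outcome 6, in both its standard and eczema-inclusive versions. Selection by primary diagnosis alone, from data that include elective admissions, lets planned admissions into an outcome meant to reflect preventable ones. The expected consequence is dilution: 0.80 becomes 0.81 to 0.83 under an assumed elective share of 5% to 15% that the intervention does not affect. The share, the 0.80 and the absence of effect on elective admissions are all assumptions, so the direction is better supported than the size.

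Outcome 7 is correctly specified by its title. The primary non-elective admission outcome has its own explicit filter and is untouched. This is a minor improvement, not a threat to the trial's main conclusions.

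**What to change.** In 10.6.1, define an ACS admission as one with a listed ICD-10 code in the primary diagnosis **and** an Admission Method code in appendix 23.6. State in 10.6.2 that the same condition applies. Apply the filter to the baseline period as well, because the model in 10.9 adjusts for the baseline rate of each endpoint. If the team wants to keep the broader count, report all admissions with a listed diagnosis as a sensitivity analysis.

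Section 10.7 needs no correction. Once 10.6.1 is restricted, its count can serve directly as the 10.7 numerator for the same population and period.

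The cost is a sentence in each subsection and one filter on a field already used for the primary outcome. The downside is slightly fewer events in outcome 6: 5% to 15% fewer under the assumed shares.

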10.6.2 ACS admissions definition including eczema

Due to the clinical emphasis of CYPHP on eczema (along with asthma and constipation), we plan an additional analysis which includes eczema in the list of ACS conditions defined above.

10.7 Proportion of non-elective admissions that are ambulatory care sensitive

Use definition above to define ACS admissions.

10.8 Summary of non-elective secondary care use

All non-elective secondary care health service use:

- Non-elective admissions
- Outpatient appointment attendances

Summarised as

- Rate: Number of activities per patient-year

- Cost of activities, based on a unit cost per activity type – cost as proxy for impact on system and family

10.9 Health Service Use Analysis Methods

The population analyses will assess the effects of the CYPHP model on health service use for CYP with any (or no) health condition.

Main analysis: cRCT Intervention vs. control analysis

- Populations: See section 8
- Time period: See section 7
- Comparator: Study arm (Intervention vs Control)
- Endpoints: Rates of health service use (listed and defined in sections 9-10)
- Summary statistics: estimate of intervention effect, estimates of covariate coefficients, 95% confidence intervals, p-values

Formal analysis: Multi-level Poisson regression model

- Individual level covariates: age, sex, IMD 2015, IDACI 2015, Borough
- Cluster level covariates: IMD 2015, IDACI 2015, baseline rate of health service use endpoint, number of CYP under 16 per cluster, Rate of paediatric OP referrals 2015-16, Borough
- Data structure:
 - Individual data: Pt Identifier, Cluster, Study arm (Intervention/Control), Number of HSU events during observation period, Observation time (days), Rate of HSU events during trial, Age at baseline, Sex, IMD 2015, IDACI 2015, Borough of GP registration, Number of HSU events during baseline period, Length of baseline period (days), Baseline rate of HSU events
 - Cluster data: IMD 2015, IDACI 2015, baseline rate of health service use endpoint, number of CYP under 16 per cluster, Rate of paediatric OP referrals 2015-16, Borough

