1.1 Trial design - Background and Rationale

Lambeth and Southwark have high levels of deprivation. These boroughs have higher than national average rates of child mortality and high unplanned health service use, and rising hospital outpatient use for children and young people (CYP) with long term conditions (LTC). The local Clinical Commissioning Groups (CCGs), Local Authorities, and Healthcare Providers have attempted to address these problems by forming The Child and Young People's Health Partnership (CYPHP) and together implementing a new model of integrated healthcare across the two boroughs. The CYPHP model aims to deliver more effective, coordinated care in primary care and community settings, and promote better self-management for CYP with common health complaints and LTCs. The CYPHP model is designed as a large-scale quality improvement initiative implementing integrated care pathways for children, for example across service provider organisations and professional groups.

This cross-organisational, system-wide, transformative, and academically rigorous approach to improving child health services aims to deliver care to traditionally hard to reach groups.

The intention of the Partnership is to roll out the full CYPHP Evelina London model of care across Lambeth and Southwark. However, due to resource limitations, implementation will occur in phases. In the first phase (~two years), approximately half of GP practices across the boroughs will implement the CYPHP model while others will offer enhanced usual care (EUC). It is expected that all the EUC practices will also adopt the CYPHP model after two years, so that all of Lambeth and Southwark will eventually be using the CYPHP model. This phased roll-out schedule offers the unique opportunity for a rigorous evaluation of the CYPHP Evelina London model of care at scale, using an opportunistic cluster Randomised Controlled Trial (cRCT) design. The unit of randomisation is the "GP hub", a group of general practices who work together to share workloads, and where the GP – paediatrician co-located clinics occur. We term these GP hubs as clusters. During the first phase of roll-out, outcomes in the CYPHP model practices can be evaluated, while the EUC practices offer a natural comparator control group. Seventy GP practices across Lambeth and Southwark, grouped into 23 clusters, were randomised to provide either the CYPHP model of care (n=11) or enhanced usual care (n=12).

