5. SAMPLE SIZE, RECRUITMENT, RANDOMISATION, AND BLINDING

5.1 Sample size and power

Population Evaluation

Pseudo-anonymised data from all children (<16 years) within participating practices will be used to analyse the impact of the CYPHP Evelina London model on health service use.

11 clusters in each arm, and an average of 3800 CYP per cluster, provides over 87% power to detect a reduction of 20% in the rate of non-elective admissions, assuming a coefficient of variation of 0.142, as explained below.

The number of CYP per cluster is estimated conservatively based on the 89382 CYP (age 0-15) registered in 2015 in the GP practices in the 23 randomised clusters. For each financial year 2013-14 – 2015-16, the baseline rate of non-elective admissions and the coefficient of variation was estimated using counts of non-elective admissions per cluster from financial years 2013-14 – 2015-16, and counts of CYP enrolled per cluster during 2013-2015. The coefficient of variation used in the sample size calculation was the mean of these three estimates. The rate of non-elective admissions was the total rate estimated by combining data from the three financial years.

Tracer Condition Evaluation

With 11 clusters in each study arm, the study team will need to recruit a minimum of 1006 CYP with a long-term tracer condition (asthma, constipation or eczema) per arm (total 2012). This number of participants will give the study 90% power to detect a mean minimum clinically important difference (MCID) of 4.5 points (standard deviation 16.5) in the primary child-health outcome tool (parental reported PEDSQL (Varni et al, 1999),² as used previously with children with chronic health conditions such as asthma (Varni et al, 2004).⁸ Intraclass coefficient (ICC) is assumed to be 0.02 based on study of quality of life in children and young people with a related condition, hay fever (Hammersley et al, 2010). Inter-cluster variation is assumed to be (0.03) based on the harmonic mean and variance of cluster size derived from GP registrations. This number also accounts for a 30% loss to follow up.

In total there are **23 clusters**, 12 in one arm and 11 in the other. As such the outlined sample size underestimates the total power as we have assumed 11 clusters in each arm.

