5.3 Randomisation

As part of the implementation of the CYPHP Evelina London model within Lambeth and Southwark, GP practices are grouped into virtual clusters. Clustering is a pragmatic clinical delivery decision, because it allows sharing of resources and holding specialist in-reach clinics without added expense to the practices. Where possible clusters were created aligned to GP Federation "neighbourhoods" or other groupings.

Of the 100 GP practices within Lambeth and Southwark, 25 took part in pilot testing of some components of the CYPHP Evelina London model of care to refine the model and test feasibility. As such these 25 practices are not randomised. All other practices are eligible to take part in the trial evaluation.

Randomisation is at the level of the primary care practice cluster. 23 clusters were randomised, by an external statistician.

Randomisation was stratified by borough, and restricted with the following restriction factors:

- Baseline Index of Multiple Deprivation (IMD) / Income Deprivation affecting children Index (IDACI) score per cluster
- CYP population <16 per GP cluster
- Paediatric OP referrals 2015-2016

These restrictions factors are believed to affect health related quality of life and patterns of health service use. Restricted randomisation on these factors helps to ensure that clusters are comparable with regards to (i) number of patients within each cluster, (ii) the socio-demographic profile of their patient population (iii) the referral patterns within clusters.

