7. STUDY TIME PERIODS

7.1 Study timeline and trial periods

CYPHP Funded: October 2016

Staff Recruitment: 1 October 2016 – 31 March 2017

Trial and Service Set up, intervention embedding: 1 April 2017 – 31 March 2018

Trial start: 1 April 2018

Trial period ends: 30 June 2021

See diagram in Appendix.

Baseline health service use data: Use annual rate(s) for financial year(s) (April-March) for 2014/15, 2015/16, 2016/17 (omitting 2017/18 as during set-up period service implementation began in some areas). Using annual rates avoids issues of seasonality. Where only one year of baseline data is needed, use 1 Apr 2016-31 Mar 2017.

Secondary analysis: Using the trial time period 1 July 2020 - 30 June 2021 (the period with most complete embedding of services).

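### Section 10.9 fixes no few-cluster inference for the primary admissions model (23 clusters, 15 residual df); an ordinary ML/normal fit, neither chosen nor excluded, would give a 95% CI about 0.74 of the correct width at the SAP's CV

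*SAP*

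**What the plan says.** Section 1.1 reports that the practices were "grouped into 23 clusters, were randomised to provide either the CYPHP model of care (n=11) or enhanced usual care (n=12"). Section 5.3 adds that "Randomisation was stratified by borough, and restricted with the following restriction factors": deprivation (IMD/IDACI), child population and paediatric outpatient referrals.

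Section 10.9 gives the analysis of all rate outcomes, including the primary one: "Formal analysis: Multi-level Poisson regression model". The output is listed as "Summary statistics: estimate of intervention effect, estimates of covariate coefficients, 95% confidence intervals, p-values". Six terms act at cluster level: "Cluster level covariates: IMD 2015, IDACI 2015, baseline rate of health service use endpoint, number of CYP under 16 per cluster", followed by the outpatient referral rate for 2015-16 and borough.

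Section 5.1 powers this outcome "assuming a coefficient of variation of 0.142, as explained below", a value taken from three baseline years: "The coefficient of variation used in the sample size calculation was the mean of these three estimates". The admission rate itself is not printed.

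Nothing in section 10.9 or elsewhere names an estimator, a reference distribution, degrees of freedom, a small-sample correction, a cluster-summary analysis or a permutation test for this outcome. Section 19 names R only. Section 11.10, the only text on what to do about within-cluster correlation, allows the random effects to be dropped when that correlation looks minimal.

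**The concern.** The arm effect is estimated between clusters, so its precision is governed by 23 units less the cluster-level parameters fitted, however many children contribute. An ordinary maximum-likelihood fit of a multi-level Poisson model ignores this twice. It estimates the between-cluster variance as if no degrees of freedom had been spent on the cluster-level terms, and it refers the estimate to a normal distribution. Both narrow the interval.

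An analyst can follow section 10.9 to the letter and report that interval. Another, equally compliant, can report one about a third wider. For the primary population outcome this should be settled before the arms are compared.

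**Working it through.** **Inputs**
- 23 clusters, 11 and 12 per arm (section 1.1).
- Between-cluster CV 0.142, unadjusted (section 5.1).
- Mean cluster size 89382/23 = 3886 children (section 5.1).
- Trial period of 39 months by section 7.1 (April 2018 start, "Trial period ends: 30 June 2021") or 27 months by section 8.1 (to June 2020). Both were run, with the 12-month secondary window of section 7.1.
- Two-sided 5% level, assumed from the 95% intervals.
- Admission rate not given: 0.03, 0.053 and 0.08 per child-year assumed.
- Residual CV after adjustment not given: range 0.03 to 0.142.

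**The plan's own figure.** The usual cluster-trial formula for rates, (c − 1) = (1.96 + z_β)²[(λ0 + λ1)/y + k²(λ0² + λ1²)]/(λ0 − λ1)², with c = 11, y = 3800 child-years, k = 0.142 and λ1 = 0.8λ0, gives 87.0% power at λ0 = 0.0531. The stated 87% is therefore attainable but cannot be confirmed independently without the rate. This is where 0.053 comes from.

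**Degrees of freedom.** Intercept, arm, IMD, IDACI, baseline rate, child population, referral rate and borough (listed at both levels, counted once) make 8 parameters. 23 − 8 = 15.

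**Closed form, when between-cluster variance dominates.** ML divides the cluster residual sum of squares by 23 instead of 15, so the standard error is too small by √(15/23) = 0.808. The t quantile on 15 df is 2.131.

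| Variance, reference | Width ratio | Type I error |
|---|---|---|
| ML, normal | 0.808 × 1.960/2.131 = 0.743 | 2P(t15 > 1.960 × 0.808) = 13.4% |
| ML, t15 | 0.808 | 2P(t15 > 2.131 × 0.808) = 10.6% |
| Unbiased, normal | 1.960/2.131 = 0.920 | 2P(t15 > 1.960) = 6.9% |
| Unbiased, t15 | 1 | 5.0% |

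**Does between-cluster variance dominate?** Its share of the variance of a cluster's log rate, at 0.053 per year over 27 months, is about 0.90 at CV 0.142, 0.54 at 0.05 and 0.29 at 0.03. The limit fits the SAP's CV well and the low CVs less well, so the model was simulated.

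**Simulation.** Poisson counts with log-normal cluster effects, 8 cluster-level terms, no treatment effect, ML with a normal reference, 4000 trials per scenario (Monte Carlo SE about 0.5 points). Ranges are over the three admission rates and, for the trial period, both lengths.

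| Residual CV | Trial period: error | Width ratio | 12 months: error | Width ratio |
|---|---|---|---|---|
| 0.142 | 12.9-13.8% | 0.74 | 11.9-14.2% | 0.73-0.74 |
| 0.05 | 10.4-13.3% | 0.74-0.77 | 7.2-11.9% | 0.76-0.82 |
| 0.03 | 7.7-11.9% | 0.75-0.83 | 5.6-8.1% | 0.82-0.86 |

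A cluster-level regression with t15 gave 4.3-5.7% in all 45 scenarios (5 CVs, 3 windows, 3 rates). Adding age group, sex and IMD quintile at individual level changed little: at 0.053 per year the ML/normal error was 14.1% (39 months) and 13.8% (27 months) at CV 0.142, and 9.2% (27 months) at CV 0.03.

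A separately coded check on log cluster rates gave a width ratio of 0.742 at CV 0.142 and 0.79 at CV 0.03 (39 months, 0.053 per year). REML with t15 covered about 94-97% there.

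**The case against.** The strongest reply is that this is silence, not a wrong statement. Section 1 calls the SAP a framework, and no sentence prescribes the fit that does the damage. That stands: every error rate above for the ML/normal fit is conditional. A reader might infer that the trial's primary interval will be too narrow, or that ML with a normal reference is the plan's default. The text supports neither. Under an unbiased variance with a normal reference the shortfall is only about 8% in width. The gap still matters, because section 10.9 goes as far as model and covariates and leaves open the step that moves the error between about 5% and about 13%.

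The size also rests on unknowns. The CV of 0.142 is an unadjusted baseline figure, while the model adjusts for baseline rate, and the admission rate is not printed. At CV 0.03 over 12 months the inflation is slight. This too stands, and is why ranges are given.

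A reader might infer that the estimator alone decides whether the interval is valid. It does not, because section 11.10 may let the team drop the random effects altogether. Whether its wording reaches back to section 10 is unclear. If it does, ignoring a between-cluster share of 0.29 or 0.54 gives errors of 2P(Z > 1.96√0.71) = 10% and 2P(Z > 1.96√0.46) = 18%.

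A reader might also infer that six cluster-level covariates are too many, or that the Poisson model must be replaced. Neither follows. The covariates are the randomisation factors plus the baseline rate and are sound. Several few-cluster methods would be valid.

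**Conclusion.** The point holds as a conditional one, and should be fixed. Section 10.9 promises an interval and p-value for the primary population outcome from 23 clusters with 15 residual df and leaves the few-cluster inference open. One ordinary reading of the stated model gives an interval at 0.74 of the correct width and 12-14% type I error at the SAP's CV. That result barely depends on the missing admission rate. With residual CV of 0.03-0.05 the trial-period figures are 0.74-0.83 and about 8-13%. These lower-CV figures depend on assumed rates of 0.03-0.08 per child-year and on a residual CV that the SAP does not state.

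**What to change.** Keep the listed covariates. Add to section 10.9 that the primary interval and p-value come from a named few-cluster method, with df equal to 23 minus the number of cluster-level parameters (15 as listed). Any one of these would serve:
- a two-stage analysis: Poisson regression on the individual covariates without arm to obtain expected counts, then linear regression of log(observed/expected) per cluster on arm and the cluster covariates, with t on 15 df;
- an equivalent mixed model with a REML-type variance and t on 15 df;
- a permutation test over the allowed restricted allocations, if that list is available (section 5.3 gives the factors but not the acceptance criteria).

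Replacing the normal by t15 on the ML fit is not enough: the error stays at about 10.6%. State also that the dropping of random effects in section 11.10 does not apply to this primary inference.

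The cost is a few sentences and a little programming. The interval becomes about 1.2 (1/0.83) to 1.35 (1/0.74) times wider than the ML/normal one over the trial period, which gives up precision that 23 clusters do not supply.
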